#### 12.2.5. Severity (Intensity)

The Investigator will assess the severity (intensity) of all AEs according to the following grading system:

- Mild AE- awareness of the event but is easily tolerated
- Moderate AE – interferes with activities of daily living
- Severe AE – incapacitating and causes inability to perform activities of daily living

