### **9.3. Exclusion Criteria**

Patients meeting any of the following exclusion criteria will not be eligible for enrollment.

1. Autoimmunity requiring immunosuppressive treatment.
2. Patients with detectable neutralizing anti-Adagen® antibodies at screening evaluation.
3. Severe thrombocytopenia (platelet count  $< 50 \times 10^9/\text{L}$ ).
4. Current participation in other therapeutic protocols for ADA-deficient combined immunodeficiency.

5. Current or prior participation in another clinical study with an investigational agent and/or use of an investigational drug in the 30 days before study entry.
6. Known planned participation in a gene-therapy study for the planned duration of this study.
7. Any condition that, in the opinion of the PI, makes the patient unsuitable for the study.
8. Inability or unwillingness to administer Adagen® or EZN-2279 on a one time per week regimen.
9. Inability to comply with the study protocol.
10. Female patients who are pregnant or lactating.
11. Female patients who are breast-feeding.
12. Female patients of childbearing potential who are not using an FDA approved birth control method.

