### 10.4.3. Laboratory Assessments

The following laboratory evaluations will be performed by the site's local laboratory as indicated in Sections 11.1 through 11.5 and Appendix 1.

- Hematology: Hemoglobin, hematocrit, WBC count, differential (includes at least: neutrophils [include bands], lymphocytes, monocytes, eosinophils, and basophils), and platelet count.
- Serum chemistry: Bicarbonate, blood urea nitrogen (BUN), calcium, chloride, creatinine, glucose, magnesium, phosphate, potassium, sodium, and total protein, albumin, alkaline phosphatase, ALT, AST, and total bilirubin.
- Urinalysis: Macroscopic (bilirubin, blood, glucose, ketones, leukocyte esterase, nitrite, pH, protein, specific gravity, and urobilinogen). Microscopic examination will include red blood cells (RBCs), WBCs, bacteria, and casts.
- Serum or urine pregnancy test: Only for female patients of child-bearing potential.

If a laboratory assessment has been performed within the specified protocol window as part of standard of care by a laboratory listed on the FDA 1572 form, it does not need to be repeated for the purpose of the protocol. The laboratory assessment result will be included on the CRF for the study.

Following the start of study treatment clinically meaningful laboratory abnormalities will be reported as an adverse event.

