### 13.2.3.5. Safety Data Analysis

Adverse Events and Serious Adverse Events – AEs will be categorized using Medical Dictionary for Regulatory Activities (MedDRA) Version 10.0 or later. The intensity of toxicities will be graded by the Investigator as mild, moderate, or severe as described in Section 12.2.5. Serious Adverse Events (SAEs) will be a subset of the overall AE analysis and may be analyzed in a similar manner.

The calculation of AE incidence will be based on the number of patients per AE category. For each patient who has multiple AEs classified to the same category, that patient will be tabulated under the maximum toxicity intensity for that AE category. The incidence of AEs will be tabulated by MedDRA system organ class and preferred term, as well as by treatment group.

An AE onset between the date of the first dose of study drug and 30 days after the last dose of study drug is considered as a treatment-emergent AE.

- Laboratory Safety Data – Hematology, chemistry, and urinalysis data will be summarized by timepoint of collection and by treatment group. In addition, out-of-normal range values will be listed.
- Other Safety Data – the results of antibodies against EZN-2279, antibodies against Adagen®, and antibodies against PEG will be summarized. The relationships between immunogenicity, PK, and the clinical toxicities will be examined as appropriate.

Concomitant medications and findings in physical examinations will be described textually as recorded in the CRF.

Descriptive statistics of vital signs measurements as well as changes from baseline will be tabulated.

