7.3 Adverse Events and Other Complications

All adverse events will be coded using the Medical Dictionary for Regulatory Activities (MedDRA) Version 16.0 or the most recent version prior to database lock. Summaries will be presented for all treatment-emergent adverse events (overall and by severity), adverse events determined by the investigator to be treatment-related (overall and by severity), serious adverse events (SAEs), adverse events causing discontinuation from study, adverse events causing discontinuation from study drug, and non-serious adverse events. In addition to being summarized as adverse events, infectious complications and hospitalizations are considered efficacy measures as are summarized in Section 6.3.

The frequency of adverse events will be summarized using descriptive statistics by system organ class (SOC), preferred term and study drug group. Patients are counted only once in each SOC category, and only once in each preferred term category.

Treatment-related adverse event summaries will include adverse events with missing relationship to study drug. For the summaries by severity, patients are counted at the greatest severity. Adverse events missing the flag indicating serious will be excluded from the summary of serious adverse events but included in the summary of non-serious adverse events.

There will be two treatment emergent adverse event summaries provided: all treatment emergent adverse events while the patient takes Adagen[®] study drug and all treatment emergent adverse events while the patient takes EZN-2279, where treatment emergent are new or worsening adverse events that occur while on the respective therapies.

Listings for all adverse events, deaths, serious adverse events, adverse events leading to discontinuation, MedDRA dictionary terms for adverse event descriptions, and adverse event preferred terms by patient number will be presented.

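### Adverse event severity is graded only by tolerability and daily function, so the by-severity tables cannot reflect the size of an asymptomatic laboratory abnormality

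*Protocol*

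**What the plan says.** - **Scope of the scale.** Protocol 12.2.5: "The Investigator will assess the severity (intensity) of all AEs according to the following grading system". No separate scale is given for laboratory events.
- **Levels.** Mild is "Mild AE- awareness of the event but is easily tolerated". Moderate "interferes with activities of daily living". Severe is "incapacitating and causes inability to perform activities of daily living".
- **Laboratory findings as adverse events.** Protocol 10.4.3: "Following the start of study treatment clinically meaningful laboratory abnormalities will be reported as an adverse event". The definition in Protocol 12.2.1 also counts abnormal laboratory findings.
- **Use in the analysis.** Protocol 13.2.3.5: "The intensity of toxicities will be graded by the Investigator as mild, moderate, or severe as described in Section 12.2.5". SAP 7.3 summarises treatment-emergent and treatment-related events by severity: "For the summaries by severity, patients are counted at the greatest severity".
- **Laboratory summaries.** SAP 7.4 gives descriptive statistics by timepoint, changes from screening (Adagen) or from the end of lead-in (EZN-2279), and listings that flag clinically significant results. Protocol 13.2.3.5 adds a listing of out-of-range values.
- **Multiple values at a visit.** SAP 10.4 uses the last non-missing one, including unscheduled assessments.
- **Another use of the word severe.** Exclusion criterion 3 in Protocol 9.3 begins "Severe thrombocytopenia (platelet count" and sets the limit at 50 × 10⁹/L.

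**The concern.** Some toxicities show first, or only, as laboratory values. A scale built on tolerance and daily function cannot rank them, yet the by-severity tables include them. A reader who takes those tables as the severity profile would not learn from them whether a laboratory event was slight or extreme.

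This matters more here than in a late-stage programme. Protocol 5.3.2 states that EZN-2279 has had no clinical studies. Protocol 5.5 promises particular attention to events seen with Adagen, and its post-approval lists include thrombocytopenia and haemolytic anaemia. Those reactions are listed regardless of relationship to the drug or the disease, and thrombocytopenia appears in both the group of at least 5% and the group of 3% to 4%. They show why laboratory toxicity deserves a usable summary; they do not give an expected rate.

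**Working it through.** The plan states no figure to reproduce, so the check is textual, with a small illustration.

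**Step 1: which events are graded.** Protocol 10.4.3 and 12.2.1 make clinically meaningful laboratory abnormalities adverse events. Protocol 12.2.5 covers all adverse events. Laboratory events are therefore on the scale.

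**Step 2: apply the levels to an event without symptoms or functional effect.**

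| Level | Test | Met? |
|---|---|---|
| Severe | Incapacity | No |
| Moderate | Interference with daily activities | No |
| Mild | Awareness, easily tolerated | At most; strictly, no awareness exists |

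The laboratory value enters none of the tests. Mild is the highest grade available, and read literally no level fits.

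**Step 3: look for another grading rule.** Protocol 13.2.3.5 refers back to 12.2.5, and SAP 7.3 adds none. Protocol 12.3 points to 12.2.1 through 12.2.4 for its definitions, severity among them, and so omits 12.2.5 without supplying an alternative. SAP 7.4 contains no toxicity grade and no shift table. SAP 6.3.3 does count clinically significant abnormal values, but only for selected immune variables.

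**Step 4: size in a six-patient table.** Assume one of six patients has an asymptomatic laboratory event that a value-based grading would class as severe, and no other severe event falls in that row.

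- By-severity table under 12.2.5: 0/6 = 0%. Exact 95% upper limit: 1 − 0.025^(1/6) = 45.9%.
- Value-based table: 1/6 = 16.7%. Exact 95% lower limit: 1 − 0.975^(1/6) = 0.4%; upper limit: the 97.5% point of Beta(2, 5) = 64.1%.

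The intervals overlap widely. The illustration shows where the event is placed; it estimates no rate.

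**Step 5: do the laboratory summaries make up for it?** Suppose one platelet count falls from 200 to 20 × 10⁹/L and the other five patients do not change.

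- Mean change = (20 − 200)/6 = −30. Median change = 0.
- The by-visit minimum is 20 only if 20 is the last value at that visit. If a repeat at the same visit is higher, SAP 10.4 takes the repeat, and the nadir drops out of the summary, though not out of the listing.

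**Step 6: how many scheduled samples are involved.** Appendix 2 shows haematology and chemistry on Adagen PK Day 1 and at T-1, T-5, T-9, T-13, T-17 and T-21: seven. SAP 10.2 assigns T-1 to Adagen, so two belong to Adagen and 7 − 2 = 5 to EZN-2279, with one more every 13 weeks in maintenance. Samples are not themselves graded; only abnormalities judged clinically meaningful become adverse events.

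**The case against.** The strongest reply is that intensity was never meant to carry medical importance. Protocol 12.2.3 separates severe from serious and names blood dyscrasias without hospitalisation as an example of an important medical event. A very low platelet count could be judged serious, reported within 24 hours, forwarded to the data and safety monitoring committee, and shown in the serious-event table. All safety data are listed, the SAP 11 display format includes minimum and maximum, and with six evaluable patients a reader can follow each patient. The mock displays are in a companion document, so a shift table may exist there. No stopping rule uses severity counts, and the same scale applies under both drugs.

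Most of this stands, and it limits the point to the summary tables. It does not repair them: the serious-event route rests on judgment and leaves the severity rows unchanged, and the by-visit range is taken after the last-value rule.

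Three stronger readings are tempting but unsupported:

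- That the plan directs asymptomatic laboratory events to be tabulated as mild. No text says so. The investigator assigns the grade, and mild is only the ceiling.
- That exclusion criterion 3 proves a misgrading. Its wording is an eligibility label, and nothing makes it govern adverse event intensity. The documents use one word in two senses.
- That the severity profile is biased towards one drug. The scale is common to both periods, and the documents give no basis for a drug-specific bias.

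**Conclusion.** The point holds as a limit on what the by-severity tables can show. A stated rule, not a missing one, keeps an asymptomatic laboratory event from reaching moderate or severe, and the text of SAP 7.4 provides no value-based summary in its place. The data are not lost, so this is a worthwhile improvement and not a threat to the trial's conclusions.

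On size, each affected patient moves a severe row by one patient: 16.7 percentage points with six patients. The as-treated denominator may be larger, because SAP 4.1 counts anyone given a lead-in dose; the step is then 1/n. This assumes that such an event occurs, is judged clinically meaningful, causes no functional effect, and would be classed severe by the limits chosen. The documents do not say how likely that is. The statement about shift tables covers the SAP text only, since the companion displays are not available.

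**What to change.** 1. **SAP 7.4:** add, for each drug period, a table of worst post-baseline laboratory grade against the grade at the start of that period (screening for Adagen, end of lead-in for EZN-2279). Use all scheduled and unscheduled values, so that the last-value rule in SAP 10.4 does not apply to this table. Name the numeric limits and fix them before the data are reviewed; limits chosen afterwards would be post hoc.
2. **SAP 7.3:** footnote that the severity tables use the functional scale of Protocol 12.2.5 and that laboratory severity is read from the new table.
3. **Wording:** state that the two uses of the word severe, in exclusion criterion 3 and in Protocol 12.2.5, must be reconciled. Do not carry the eligibility cutoff over as an adverse event grade.

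The cost is one table, a footnote and a short paragraph, all from values already collected. There are two downsides. The report gains a second grading basis, which the footnote explains. Also, a worst value tends to be more extreme when more samples are taken. With two scheduled samples after screening under Adagen and five or more under EZN-2279, the two panels should be read as descriptions and not compared directly.

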### 12.3. Reporting Adverse Events

All new events, as well as those that worsen in intensity or frequency relative to baseline, which occur must be captured. The Investigator or his/her staff should elicit information regarding the occurrence of adverse events through information volunteered by the patient, open-ended questioning of the patient, physical examination results and review of laboratory results.

Information to be recorded for each AE includes:

- A medical diagnosis of the event (if a medical diagnosis cannot be determined, a description of each sign or symptom characterizing the event should be recorded)
- The date and time of onset of the event
- The date and time of resolution of the event
- Assessments of severity, causal relationship, and seriousness of the adverse event (see definitions in Section 12.2.1 through 12.2.4)
- Action(s) taken (if any) for management of the adverse event, including but not limited to change in the study drug administration (e.g., temporary interruption in dosing, dose reduction); drug treatment; non-drug treatment; diagnostic procedures performed
- Outcome of the adverse event: e.g., patient recovered without sequelae; patient recovered with sequelae; event ongoing; patient died

If a medical condition is known to have caused the injury or accident (e.g., a fall secondary to dizziness), the medical condition (dizziness) and the medical condition resultant to the fall (hip fracture) should be reported as two separate AEs. The act of falling (i.e., fall) should be recorded as part of the event term in the CRF.

All adverse events will be followed until resolution, stabilization, or for 30 days after last dose of study drug, whichever occurs first.

#### 12.4. Reporting Serious Adverse Events

All serious adverse events (SAEs), regardless of relationship to study drug, must be reported to Leadiant Biosciences as described below.

- Serious adverse events that are fatal or life-threatening must be reported to Leadiant Biosciences or their designee by telephone *immediately* after site personnel first become aware of the event. Within 24 hours, the Leadiant Biosciences Serious Adverse Event Form must be faxed to the medical monitor or designee regardless of whether full information regarding the event is known or not. If full information is not known, additional follow-up by the Investigator will be required.
- All other serious adverse events must be reported to the Leadiant Biosciences medical monitor or designee within 24 hours by phone, e-mail or fax after becoming aware of the event. Within 48 hours, the Leadiant Biosciences Serious Adverse Event Form must be faxed to the medical monitor or designee regardless of whether full information regarding the event is known or not. If full information is not known, additional follow-up by the Investigator will be required.

Report all SAEs to the Leadiant Biosciences safety representative listed in the Study Reference Manual.

All SAEs will be evaluated by the Leadiant Biosciences Medical Monitor or designee. If meeting the requirements for expedited reporting (i.e., serious, unexpected and related), Leadiant Biosciences will so report the adverse event to all regulatory authorities with jurisdiction over ongoing trials with the study drug and to all other investigators involved in clinical trials with EZN-2279.

The Investigator must report all SAEs reported by Leadiant Biosciences to regulatory authorities in an expedited manner to the reviewing IRB. For all other SAEs, the Investigator must report all serious adverse events in accordance with the requirements of the reviewing IRB.

Leadiant Biosciences will forward all reports of SAEs to the DSMC and the Lead PI.

#### 12.4.1. Reporting of Other Non-serious Events

In addition to reporting of SAEs, the following are specific conditions defined by Leadiant Biosciences for this study, which may or may not be SAEs (i.e., as defined above [Section 12.2.3]). These conditions, whether serious or not, are to be reported to Leadiant Biosciences within 48-hours using the Leadiant Biosciences Serious Adverse Event Form:

- All signs and symptoms of an allergic reaction that may not necessarily be deemed serious. For example: urticaria, facial swelling, lip swelling, orbital swelling, rash, pruritus, nasal congestion, injection site reaction, etc., should be reported to Leadiant Biosciences as “Special AE Report.” Note: An anaphylactic reaction meets the definition of “serious” and would, therefore, be reported as an SAE.

#### 12.5. Reporting of Pregnancy

If a patient becomes pregnant or is found to be pregnant while on the study, the Leadiant Biosciences medical monitor or designee will be contacted to discuss the management of the patient, which may include discontinuation of study drug.

Although pregnancy is not a serious adverse event all pregnancies occurring during this study will be reported to the Leadiant Biosciences Drug Safety within 48 hours of becoming aware of the pregnancy and complete and submit a pregnancy report form.

All pregnancies will be followed until delivery or pregnancy termination for maternal and fetal outcomes.

### 13. STATISTICS

#### 13.1. Sample Size Determination

The sample size of six patients accounts for more than 5% of the entire eligible patient population worldwide and 10% of the entire eligible patient population in the United States.

The study will enroll a sufficient number of patients with ADA-SCID who meet all study entry criteria to assure six (6) patients are evaluable, where evaluable is defined as completing the EZN-2279 treatment period and providing primary study endpoint data.

The patients enrolled in this study all will have achieved metabolic detoxification with Adagen® prior to initiating EZN-2279 treatment. Patients are expected to maintain the target trough total erythrocyte dAXP concentration with EZN-2279 at a planned success rate of 100%. Therefore, the usual statistical sample size calculations using precision analysis, power analysis, or probability are not applicable due to zero variability.

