3.2 Sample Size and Power Considerations

The study will enroll a sufficient number of patients with ADA-SCID who meet all study entry criteria described to assure six (6) patients are evaluable, where evaluable is defined as completing the EZN-2279 treatment period (Week T-21) and providing primary study endpoint data.

More than 6 patients may be enrolled to achieve the required number of evaluable patients. It is expected that up to 12 study centers will participate in the study. There are no restrictions on the number of patients a single study center may enroll.

The sample size of six patients accounts for more than 5% of the entire eligible patient population worldwide and 10% of the entire eligible patient population in the United States.

The patients enrolled in this study all will have achieved metabolic detoxification with weekly Adagen® dosing prior to initiating EZN-2279 treatment. All patients are expected to maintain the target trough total erythrocyte dAXP concentration with EZN-2279. Therefore, the usual statistical sample size calculations using precision analysis, power analysis, or probability are not applicable due to zero variability.

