4.3 Completer Population

The completer population, defined as all patients who have received EZN-2279 through the primary endpoint visit (i.e., through Week T-21) will be the analysis set for evaluating efficacy endpoints because the complete EZN-2279 treatment period is required to establish maintenance of the target trough levels, immune function status and other efficacy endpoints.

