6. EFFICACY ANALYSIS

The completer population will be used for the primary efficacy analysis, because the endpoint cannot be evaluated until T-21, and the as-treated population will be used for a sensitivity analysis of the primary efficacy endpoint. The as-treated population will be used for all other efficacy analyses, unless otherwise noted. Summaries will only be presented for the EZN-2279 group. Efficacy is evaluated in comparison to the Adagen® Lead in period ('baseline'). All efficacy data will be listed.

Given the sample size, all efficacy analyses will be descriptive (i.e., no statistical testing and no reported p-values), although 95% confidence intervals (CI) may be presented to show the variability of estimates.

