6.2 Primary Endpoint and Analysis

The primary endpoint is the proportion of patients achieving metabolic detoxification, assessed from trough dAXP samples obtained at Weeks T-15, T-17, T-19, and T-21. Metabolic detoxification is defined as a trough dAXP concentration equal to or below 0.02 µmol/mL.

Trough dAXP level will be summarized at each above time point. Maintenance of detoxification is defined as meeting the target trough levels for each of the 4 weeks listed above in the EZN-2279 treatment period. The proportion of patients meeting this definition of maintenance will be summarized.

Trough dAXP level will be summarized at last observed value as a sensitivity analysis using the as-treated population.

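### Protocol 13.1 and SAP 3.2 rest the lack of a sample size calculation on zero variability, which a planned 100% rate does not give; the SAP requires no interval for the primary proportion (6/6 would be 54.1–100%)

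*Protocol*

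**What the plan says.** Protocol 13.1 defines an evaluable patient as one who finishes the EZN-2279 treatment period and supplies primary endpoint data, and aims for six. It expresses six as a share of the eligible population (over 5% worldwide, 10% in the United States). It then states: "Patients are expected to maintain the target trough total erythrocyte dAXP concentration with EZN-2279 at a planned success rate of 100" percent, and concludes that "the usual statistical sample size calculations using precision analysis, power analysis, or probability are not applicable due to zero variability". SAP 3.2 expects all patients to stay on target and ends the same way: "precision analysis, power analysis, or probability are not applicable due to zero variability".

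On the analysis:

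- SAP 4.3 says the completer population (dosed through Week T-21) "will be the analysis set for evaluating efficacy endpoints". SAP 6 narrows this: "The completer population will be used for the primary efficacy analysis, because the endpoint cannot be evaluated until T-21", with the as-treated population used for a sensitivity analysis and for most other efficacy analyses.
- SAP 6 makes all efficacy analyses descriptive, without tests or p-values, and adds that "95% confidence intervals (CI) may be presented to show the variability of estimates".
- SAP 6.2 takes the endpoint from trough dAXP at Weeks T-15, T-17, T-19 and T-21, with a target of at most 0.02 µmol/mL. "Maintenance of detoxification is defined as meeting the target trough levels for each of the 4 weeks listed above in the EZN-2279 treatment period". The output is: "The proportion of patients meeting this definition of maintenance will be summarized". No interval is mentioned there, nor in Protocol 13.2.3.4.
- Protocol 13.2.2 describes the primary endpoint as covering both patients who reach detoxification and patients who do not.
- Under Protocol 9.5.3, a patient who does not complete Week T-21 is unevaluable and is replaced.

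**The concern.** The argument moves from an expected rate to a property of the data. Expecting every patient to succeed does not mean that the observed proportion has no sampling error. Protocol 5.3.2 says no clinical study of EZN-2279 has been performed, so the documents hold no clinical data on this product behind the 100%. Detoxification on Adagen before the switch is a response to a different product. Protocol 13.2.2 allows for non-responders, and SAP 6 itself speaks of the variability of estimates.

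What is at stake is how the main result reads. The outcome the plan expects, all successes, is the one where a bare percentage most hides how little six patients can show. This is a Phase 3 trial, and Protocol 13.3 and SAP 6.4 provide for an interim analysis, intended for a licence application, with as few as three patients through Week T-21.

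**Working it through.** **Inputs.** n = 6 evaluable (Protocol 13.1, SAP 3.2); planned rate 100% (Protocol 13.1); interval level 95% (SAP 6), taken as two-sided in line with Protocol 13.2.1; minimum interim n = 3 (Protocol 13.3, SAP 6.4). The documents give no power, precision target, null rate or margin, so six cannot be derived from them. The population shares only imply fewer than 6/0.05 = 120 eligible patients worldwide and 6/0.10 = 60 in the United States.

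**1. Where zero variability can come from.** The documents show no formula. The route that yields it is the plug-in standard error at p = 1: √(p(1 − p)/n) = √(1 × 0/6) = 0. That is a feature of this formula at the boundary, not of the trial.

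**2. Exact precision at the planned size.** When all n patients succeed, the Clopper-Pearson lower limit is 0.025^(1/n) and the upper limit is 1. For 5/6 the limits are the 0.025 quantile of Beta(5, 2) and the 0.975 quantile of Beta(6, 1).

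| Result | Calculation | Exact two-sided 95% CI |
|---|---|---|
| 6/6 | 0.025^(1/6) = 0.5407 | 54.1–100% |
| 5/6 | 0.3588; 0.9958 | 35.9–99.6% |
| 3/3 (interim minimum) | 0.025^(1/3) = 0.2924 | 29.2–100% |
| 7/7 (if more than six are evaluable) | 0.025^(1/7) = 0.5904 | 59.0–100% |

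The choice of method does not remove the uncertainty: the Wilson lower limit at 6/6 is 6/(6 + 1.96²) = 61.0%.

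**3. Probability also applies.** The chance of 6/6 is p⁶ for a true rate p:

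- p = 0.60: 0.047
- p = 0.80: 0.26
- p = 0.90: 0.53
- p = 0.95: 0.74

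The planned result would therefore be unremarkable at true rates well below 100%.

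**4. A precision-based sample size exists even if every patient succeeds.** Requiring 0.025^(1/n) ≥ L gives n ≥ ln(0.025)/ln(L). For L = 70%, 80% and 90%, n is 11, 17 and 36. These targets are illustrations only; the documents set none. They show that the calculation can be done, not that it should have fixed n.

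**The case against.** The strongest reply is that both documents speak of the *usual* sample size calculations, and the usual variance-based formulas do break down at p = 1. That stands as far as it goes, and the sentence should not be read as denying that any interval can ever be computed. But it also names precision and probability, and steps 2 to 4 show that both remain available through exact methods.

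Second, SAP 6 does mention 95% confidence intervals, and the sentence covers all efficacy analyses, the primary one included. So it would be wrong to say that the SAP ignores intervals. The accurate statement is that they are optional and that no method is named. The mock displays (SAP Appendix B) and the separate statistical plan for the licence application are not among the documents here and may say more.

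Third, efficacy is descriptive, Protocol 13.4 sets no statistical criteria for termination, all efficacy data are listed, and dAXP is summarized at each of the four weeks. A careful reader could compute the interval. This stands and limits the consequence to reporting.

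A reader might infer more than this, and the documents do not support it:

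- *That six is the wrong number or that a test is needed.* Six may well be all that is feasible, although the documents do not say so: Protocol 5.4 uses rarity to explain the absence of a randomized control, and Protocol 13.1 gives only population shares.
- *That a zero-width interval of 100–100% is planned.* The SAP text does not rule one out, but nothing shows it is intended.

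**Conclusion.** The stated reason in Protocol 13.1 and SAP 3.2 is wrong and should be replaced. The sample size itself is not shown to be wrong. The expected result of 6/6 is compatible, at the two-sided 95% level, with true rates down to 54.1%, and 3/3 at an interim with rates down to 29.2%. As written, the SAP lets either be reported simply as 100%.

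The figures assume:

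- independent patients;
- success defined as meeting the dAXP target at all four weeks. SAP 6.2 attaches that rule to maintenance, while the endpoint sentence speaks of achieving detoxification;
- exactly six patients in the denominator, each with the data needed. A completer under SAP 4.3 need only have been dosed through Week T-21, whereas an evaluable patient must also supply primary endpoint data, so the two counts can differ;
- conditioning on completion. Because non-completers are replaced, the interval describes patients who reached Week T-21, not everyone who started EZN-2279.

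**What to change.** 1. In SAP 3.2, and in Protocol 13.1 at the next amendment, replace the zero-variability sentence with:

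   *N = 6 evaluable patients is not based on a power or precision calculation [sponsor to confirm the reason]. With six evaluable patients (completing Week T-21 and providing primary endpoint data; patients who do not complete are replaced), the exact (Clopper-Pearson) two-sided 95% CI for the proportion meeting trough dAXP ≤0.02 µmol/mL at all of Weeks T-15, T-17, T-19 and T-21 would be 54.1–100% for 6/6 and 35.9–99.6% for 5/6.*

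2. Add to SAP 6.2:

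   *An exact (Clopper-Pearson) two-sided 95% CI will be presented for the proportion of patients in the primary analysis population meeting the target at all four weeks, with the number of patients replaced before Week T-21 reported alongside.*

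   The optional sentence in SAP 6 can stay for the other endpoints.

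3. Apply the same interval to any interim or licence-application presentation of this proportion, unless the separate analysis plan for that application already does so.

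**Cost.** Short edits to two SAP sections and possibly one line in the licence-application plan. The protocol change needs a written amendment and IRB approval (Protocol 14.1.1), so it can wait for the next one. The only real downside is a less favourable statement of certainty. Naming the method before results are known also removes any choice of interval afterwards.
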